### 17.5 Missing Data

17.5.1 We will handle missing data values with a 3-step process. First, the dropout rates will be compared across the groups with chi-square analyses to assess systematic differences due to condition. Second, demographic and dependent variables will be examined for their relationship to dropout. Those variables related to dropout status will be used to impute missing values for use in the analyses described (via SPSS Missing Items Analysis). Finally, comparison of the completers vs. imputation analyses will yield an additional estimate of the effect of dropouts on hypothesis tests.

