#### 4.1.3 Executive Functions

Type: Primary

Time Frame: Baseline (T1), 1 Month (T2) and 3 Months (T3)

Brief Description: The last 8 minutes of the drive starts in a residential area with low speeds (15-30 mph) and then progresses to city with speeds 30-45 mph. This part of the drive will occur in a suburban environment, daytime driving with minimal lead, following and oncoming traffic, and some pedestrians and cyclists. Streets will be surrounded by buildings and strip malls. Executive functions are measured by providing the driver with an instruction before the drive (e.g. to turn into a McDonald's, pull into a parking bay, park the car (vehicle positioning), and when it is safe to do so, back up out of the parking bay (visual scanning) exit the lot and merge into the flow of traffic. Executive functions are measured via visual scanning (yes/no), speed regulation (mph over or under the speed limit), adjustment to stimuli (notice the McDonald's (yes/no), slow down (mph), signaling (yes/no), vehicle positioning (buffer around the vehicle yes/no), and gap acceptance (narrow or tight via ms).

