We will recruit N=60 participants total. Participants will be eligible for the current study if they: a) report severe or chronic pain; b) are age 50 or older; c) are newly registered for the Medical Marijuana Registry in the State of Florida; d) have no prior history of medical marijuana use; e) can communicate in English; and f) are willing and able to complete study procedures or if they meet control group criteria: (n=30) Medical Marijuana Users **or** (n=30) Age, Gender, Race Matched Controls. Persons will be ineligible if they: a) meet

**PROTOCOL TITLE:** Medical Marijuana Use and Driving Performance: A Test of Psychomotor Function in Adults 50 and Older.

criteria for current or past alcohol and/or illicit drug dependence; b) have vertigo or any vestibular systems dysfunction (due to the to develop simulator adaptation syndrome); c) screen high on the simulator sickness prescreen; d) use contraindicated medication (benzodiazepines, beta blockers, antihistamines, or sedatives) from which they cannot abstain due to medical reasons; and/or e) are planning to move out of the area within 6 months.

We will recruit patients in the control group within the local community. This will happen by placing recruitment flyers in public places (i.e. grocery stores, libraries, senior living communities, etc.). Additionally, we will utilize Consent2Share, an initiative of the UF Integrated Data Repository (IDR) and supported by UF CTSI (Clinical and Translational Science Institute) that allows for a large group of potential research participants who have consented to be re-contacted for future research studies. The control group will be matched by age, gender and race. Control subjects will be ineligible if they: a) meet criteria for current or past alcohol and/or illicit drug dependence; b) have vertigo or any vestibular systems dysfunction (due to the to develop simulator adaptation syndrome); c) screen high on the simulator sickness prescreen; d) use contraindicated medication (benzodiazepines, beta blockers, antihistamines, or sedatives) from which they cannot abstain due to medical reasons; and/or e) are planning to move out of the area within 6 months, f.) have a history of marijuana use. Control subjects will be used to ensure results are not attributed to a simple change in time. Results will provide evidence for the effects of medical marijuana use on the real work task among adults 50 and older.

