**6.2 Baseline Assessment Procedures.** Once eligibility has been met, participants will be scheduled for their baseline assessment in the week prior to starting medical marijuana. At the baseline appointment, participants will be greeted by a study research assistant who will introduce the study and provide the patient with informed consent. We have standardized the informed consent procedure to ensure that participants not only understand the informed consent process but also fully understand what is being asked of them during the study period. Following informed consent, participants will complete the baseline assessment. The baseline assessment will consist of a battery of psychosocial measures, a cognitive test, a 5 minute simulator adaptation drive, and a 15 minute main drive. Adherence to simulator sickness protocol will be ensured before, during, and after the drives. In an effort to maintain engagement, participants will be contacted via telephone 60 days post-baseline to complete a 3-item questionnaire regarding significant life changes as well as a pain scale. We will also request permission to extract needed data on an ongoing basis from patients' electronic medical records.

**6.3 Training of Research Assistants.** All study research assistants will be trained in Good Research Practices, Safety Concerns in Dealing with Patients, and Data Collection Procedures. The training will also cover 1) familiarization with study aims, instruments, and assessment procedures specific to the study; 2) confidentiality and informed consent, data integrity, and data security; 3) observation of mock assessment conducted by the project director; and 5) a

PROTOCOL TITLE: Medical Marijuana Use and Driving Performance: A Test of Psychomotor Function in Adults 50 and Older.

practice assessment with the project director. Research assistants will also receive “red flag” training on how to recognize and respond to danger to self and others, child abuse, elder/dependent adult abuse, and domestic violence.

Several procedures will help standardize data collection and encourage accuracy and honesty in reporting, as follows: 1) trained research assistants will conduct the assessments; 2) a private interview setting will minimize distractions and ensure confidentiality; and 3) research assistants will remind participants of the confidentiality of the information that they provide.

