## **17.0 Data Management\* and Confidentiality**

17.1 **Test of Aim 1 (Driving Simulator):** Between group (medical marijuana users vs controls) comparisons will first be examined using independent samples t-test (controlling for unequal variances using Levene's test) or Mann-Whitney U tests if the data are nonparametric. Repeated measures ANOVA will be used to examine within participants differences on measures at all 3 time points in order to answer the question of whether medical marijuana impacts response time, divided attention, and executive functions.

Limitations may be related to the distribution of the dependent and independent variables. Possible mitigation approaches include creating a dichotomous variable of high versus low for outcomes and using logistic regression or other functional form as dictated by the distribution of the dependent and independent variables.

17.2 **Test of Aim 2 (Adverse Effects):** To describe factors associated with adverse effects we will report the number of adverse effects reported by participants at time points 2 and 3. Adverse Effects will be defined as both a count variable and a binary variable such that absence or presence of adverse effects will be coded as 0/1 respectively. We will then use Poisson and Logistic regression methods to examine analyze the bivariate association between dosage, frequency of use, route of administration (pills, vape, etc.), and type of product (THC v. CBD). Limitations may be related to the frequency and distribution of events leading to complete or quasi-separation of data points. Possible mitigations would be re-categorization of explanatory variables, exact or firth regression, or a different functional form of the model. The goal of aim 2 is to examine the strength of the association between factors of medical marijuana use and adverse effects. As there may be insufficient power for statistical

PROTOCOL TITLE: Medical Marijuana Use and Driving Performance: A Test of Psychomotor Function in Adults 50 and Older.

significance, effect size estimates (Cohen's d) will be used to examine the strength of the association between variables.

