### 17.3 Power Analysis

17.4 We compute the power to detect a medium effect size of 0.5 standard deviations across groups. Assuming a correlation of 0.2 across the repeated measures at three time points, the standard deviation of the average of three measures is 0.683 times the standard deviation of one measure. Therefore, with 31 per group we can detect a difference in this average of 0.5 times the standard deviation of one measure, using a two-sided test with 80% power. We calculated Cohen's d using [name] prior work that examined total driving errors and specific errors (Lane maintenance) in healthy controls ( $M= 24.08$   $SD=12.38$ ) and ( $M= 5.78$   $SD=4.26$ ) versus Parkinson patients ( $M=31.99$   $SD=22.01$ ) and ( $M=10.23$   $SD= 9.26$ ) which yielded a Cohen's d of .46-.65 (medium effect size); therefore we will be powered to detect this medium effect size.

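### Section 17.5 does not require group, or the outcomes at all three visits, in the imputation model; if group is left out, the imputed Aim 1 difference will usually be attenuated

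*Combined protocol and SAP*

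**What the plan says.** Section 17.5 sets out three steps. The first compares dropout between the groups by chi-square. In the second, "demographic and dependent variables will be examined for their relationship to dropout", and then "Those variables related to dropout status will be used to impute missing values for use in the analyses described". In the third, "comparison of the completers vs. imputation analyses will yield an additional estimate of the effect of dropouts on hypothesis tests". Group appears only in the first step. The section gives no threshold for counting a variable as related to dropout and no expected dropout rate. It also does not say whether imputation is single or multiple.

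The analyses that these imputed values feed are in 17.1: "Between group (medical marijuana users vs controls) comparisons will first be examined using independent samples t-test", followed by a repeated measures ANOVA over the three visits. Section 17.4 powers the study on the three-visit average: "with 31 per group we can detect a difference in this average of 0.5 times the standard deviation of one measure".

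Two design features bear on what could stand in for group. In 6.1, "The control group will be matched by age, gender and race". In 6.2, "participants will be scheduled for their baseline assessment in the week prior to starting medical marijuana", so T1 precedes exposure.

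**The concern.** An imputation model should contain the variables of the analysis it serves. A variable's relation to dropout is a reason to add it to that model, but lack of such a relation is no reason to leave out group. When group is absent, missing values of users and controls are drawn from one common distribution. The imputed part of the data then carries little of the group difference that 17.1 tests.

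This happens even when dropout is equal in the two groups, which is when the 17.5 rule gives no cause to select group. Age, gender and race cannot replace it, because controls are matched on them. T1 cannot carry an effect of exposure that has not yet happened.

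An effect on driving would then be easier to miss. The third step reads any gap between completers and imputed results as the effect of dropout, so a gap created by the imputation model could be misattributed.

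**Working it through.** **Inputs from the protocol.** Effect 0.5 SD, correlation 0.2 between visits, two-sided test, 80% power, 31 per group (17.4); 30 per group recruited (6.1).

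**Assumptions.** Alpha 0.05; continuous outcome with SD 1; T1 complete; a proportion m missing T3, with m = 10/20/30%; half of these also missing T2; dropout random and equal between groups unless stated.

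**1. The plan's own figure.** SD of the average = √((1 + 2×0.2)/3) = 0.683, as stated. Noncentral t power is 0.809 at 31 per group and 0.796 at 30, so 31 reproduces. The standard error at 30 per group is 0.683×√(2/30) = 0.18.

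**2. No useful predictors, group omitted.** Imputed values carry no group difference, so a visit with fraction m missing keeps (1 − m) of its difference.
- Constant 0.5: [0.5 + 0.5(1 − m/2) + 0.5(1 − m)]/3 = 0.50 − 0.25m, giving 0.475/0.450/0.425.
- Effect 0/0.75/0.75: 0.50 − 0.375m, giving 0.462/0.425/0.387.

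**3. Observed outcomes as predictors, group omitted, constant 0.5.** This is kinder to the plan, because earlier outcomes carry some group information.
- Pooling the groups, each visit has variance 1 + 0.5²/4 = 1.0625 and covariance 0.2 + 0.0625 = 0.2625.
- Missing T2 and T3: slope on T1 is 0.2625/1.0625 = 0.247, so the imputed difference is 0.247×0.5 = 0.124.
- Missing T3 only: slope on each of T1 and T2 is 0.2625/(1.0625 + 0.2625) = 0.198, so the imputed difference is 0.198×(0.5 + 0.5) = 0.198.
- Average = 0.50 − (m/6)[(0.5 − 0.124) + (0.5 − 0.198) + (0.5 − 0.124)] = 0.50 − 0.176m, giving 0.482/0.465/0.447.

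The same steps for 0/0.75/0.75 give imputed differences of 0 (T2 and T3 missing) and 0.205 (T3 only). The average is 0.50 − 0.341m, or 0.466/0.432/0.398.

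**4. Simulation at 30 per group** (20 imputations, Rubin's rules, two-sided 5% t-test; 6,000 trials for the constant effect, 3,000 for the other).

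| Setting, three-visit average, true 0.50 | 10% | 20% | 30% |
|---|---|---|---|
| Constant 0.5, without group: estimate | 0.484 | 0.465 | 0.448 |
| Constant 0.5, without group: power | 76% | 69% | 65% |
| Constant 0.5, with group: power | 78% | 75% | 73% |
| 0/0.75/0.75, without group: estimate | 0.464 | 0.425 | 0.393 |
| 0/0.75/0.75, without group: power | 71% | 61% | 50% |
| 0/0.75/0.75, with group: estimate | 0.499 | 0.494 | 0.496 |
| 0/0.75/0.75, with group: power | 77% | 73% | 71% |
| 0/0.75/0.75, completers: estimate | 0.499 | 0.494 | 0.493 |
| 0/0.75/0.75, completers: power | 75% | 68% | 62% |

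The estimates agree with step 3. If dropout depends on the T1 score, the 0/0.75/0.75 estimates are 0.460/0.427/0.397 without group and 0.493/0.498/0.502 with it.

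**5. Would step 1 bring group in?** The threshold is unstated. If it is p<0.05, the chi-square flags group in about 5% of trials with equal dropout. With 10% against 30% dropout it does so in about 50% (37% with continuity correction). At p<0.20 the figures are about 22% and 78%.

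**6. Limits on direction.**
- With no group difference at any visit, the imputed difference stays at zero.
- With differences of 1.0/0.25/0.25 (average 0.50), the step 3 method gives 0.498/0.496/0.494, so there is practically no bias.
- With 0.8 at T1 and T2, 0.3 at T3, correlation 0.5 and 20% missing, the imputed T3 difference is 0.32 to 0.34, which is away from zero.

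**The case against.** A reader might infer that 17.5 keeps group out of the imputation. The text does not say so: group is tested against dropout in step 1 and could count as a related variable. The defect is that its entry is left to a screen with no threshold, and that screen will not select it when dropout is similar in the two groups.

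A reader might also infer that the bias is always toward zero. The documents do not support that. The groups are not randomised, and pain is an entry criterion for users, while controls are described only as matched on age, gender and race. T1 may therefore differ between the groups and carry group information. The 1.0/0.25/0.25 pattern is deliberately extreme, but it shows that the bias can vanish, and the last case in the working shows that it can reverse.

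Three points about size stand:
- Section 17.4 gives no visit pattern. The constant effect is the milder reading, and its power loss of about 2 to 8 points should be quoted first.
- The power figures assume multiple imputation, which the plan does not state. With one stochastic imputation, power without group was about 76/72/70% for the constant effect. Single imputation has its own fault: it rejected in 6 to 8% of trials under no effect, even with group included.
- With purely random dropout the outcomes would usually not be flagged either, so imputing from them is not strictly the 17.5 rule. It is the favourable choice, as steps 2 and 3 show. If nothing is flagged, the section supplies no imputation model at all.

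The planned completers analysis is a real but partial safeguard. It was unbiased in the table above and would reveal a discrepancy. It does not correct the imputed result, and it has less power than imputation with group.

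**Conclusion.** The point holds in conditional form. Section 17.5 should require group and all three outcomes in the imputation model and does not. If group is omitted and the groups differ after exposure, the imputed Aim 1 difference will usually be attenuated. At 10/20/30% dropout the three-visit average of 0.50 SD loses about 0.02/0.03/0.05 SD if the effect is constant, and about 0.04/0.07/0.11 SD if it appears only after T1. Against a standard error of 0.18 the loss at 10% is small; at 30% it costs about 8 power points in the constant case.

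These sizes rest on an assumed dropout rate and missingness pattern, correlation 0.2, multiple imputation and a continuous outcome. Yes/no and count outcomes were not simulated. The change is one the plan should make; nothing here shows that the Aim 1 result would be invalid. Confidence is medium, because the size depends on dropout and on T1 differences that the protocol does not give.

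**What to change.** In 17.5, state that the imputation model always contains group and the outcome at T1, T2 and T3, whatever their relation to dropout. Add dropout-related variables as auxiliaries, and age, gender and race where the sample allows. Specify multiple imputation with a stated number of datasets (for example 20 to 50), pooled by Rubin's rules. Use a model suited to each outcome type, since the endpoints mix scales, for example "Executive functions are measured via visual scanning (yes/no), speed regulation (mph over or under the speed limit".

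For continuous outcomes, a likelihood mixed model with group, visit and group-by-visit on all observed data is an acceptable alternative; 17.1 would then need rewording.

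In the 0/0.75/0.75 setting, imputing with group, the outcomes, age, gender and race gave 0.499/0.493/0.496 with power 77/73/69%. Rejection under no effect was 4.7/4.6/5.0%.

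The cost is one paragraph and some extra analysis work, with no new data. In about 60 people, sparse yes/no items may not support every auxiliary variable. Group and the three outcomes should then be kept and auxiliaries dropped first.

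### Section 17.5 feeds imputed visits into the t-test and repeated measures ANOVA without stating multiple imputation, pooling, or whether group is a predictor; single imputation would distort error rates or the effect

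*Combined protocol and SAP*

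**What the plan says.** Section 17.5 sets out three steps. The first is a check by group: "First, the dropout rates will be compared across the groups with chi-square analyses to assess systematic differences due to condition". The second screens for predictors: "Second, demographic and dependent variables will be examined for their relationship to dropout". It then imputes: "Those variables related to dropout status will be used to impute missing values for use in the analyses described (via SPSS Missing Items Analysis"). The last step is a check: "comparison of the completers vs. imputation analyses will yield an additional estimate of the effect of dropouts on hypothesis tests".

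The analyses that receive the imputed values are in 17.1. Between-group "comparisons will first be examined using independent samples t-test", or Mann-Whitney where the data call for it. Then "Repeated measures ANOVA will be used to examine within participants differences on measures at all 3 time points".

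No section says whether one or several imputed data sets are made, how results would be combined, whether group or earlier visits enter the imputation model, how much dropout is expected, or what alpha is. Section 17.1 does not say at which visit the t-test is run.

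**The concern.** A missing value carries no information of its own. If it is filled in once and the completed data set goes into an ordinary t-test or ANOVA, the standard error uses the full sample size and, usually, a variance that is too small. Repeated measures ANOVA in its usual form needs all three visits from each participant, so the choice of ANOVA is itself what creates the need to impute.

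At stake are the p-values and intervals for H1a to H1c. The final step of 17.5 could also mislead: an imputed analysis may look sharper than the completers' analysis only because filled-in values were counted as data.

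**Working it through.** **Inputs.** From the documents: 30 per group (6.1); correlation 0.2 between visits, a 0.5 SD effect, and the average of three visits as the powered quantity (17.4). Assumed, because the documents are silent: alpha 5% two-sided; dropout at random, 10% by T2 and 20% by T3; a single imputation. Correlation 0.5 was also tried.

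**1. The plan's own figure.** Section 17.4 says: "We compute the power to detect a medium effect size of 0.5 standard deviations across groups". The SD of the three-visit average is sqrt((1 + 2 x 0.2)/3) = 0.683 of one measure's SD. The t-test solution is 30.3, rounded up to the stated 31 per group, with power 0.809. The figure reproduces. It makes no allowance for missing visits.

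**2. Simple case by hand: mean fill at T3.** With 20% missing, 24 of 30 per group are observed.

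- *Fill with the group's own mean.* The true variance of a group mean is s²/24. The analysis reports about 0.8s²/30, because filled values add no spread. The ratio of reported to true SE is sqrt(0.8 x 24/30) = sqrt(0.64) = 0.80. The rejection rate under no effect is 2 x (1 - Φ(1.96 x 0.80)) = 2 x (1 - Φ(1.568)) = 11.7%.
- *Fill with the overall mean, group ignored.* The estimated difference is 0.8 times the observed one, so its true variance per group is 0.64s²/24 = 0.0267s². The reported variance is 0.8s²/30 = 0.0267s². The ratio is 1 and the rate stays at 5%. The price is the estimate: 0.8 x 0.5 = 0.40 SD instead of 0.50.

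So whether group is a predictor decides which error appears.

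**3. Simulation under no effect.** The setting is 30 per group, monotone random dropout of 10% at T2 and 20% at T3, correlation 0.2 and 0.5, and one regression imputation from earlier visits, with or without a random residual.

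| Test (nominal 5%) | Group in imputation model | Group left out |
|---|---|---|
| T3 t-test | about 9-12% | about 5-6% |
| Group-by-visit (ANOVA) | about 9-10% | about 5% |
| Three-visit average by group | about 6-8% | about 5-6% |

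The ANOVA visit effect rejects about 9-11% with group left out. The T3 mean then rests on 2 x 24 = 48 observed values but is analysed as 60.

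**4. Dependence on the missing fraction.** With only T3 missing, correlation 0.2, and regression fill with group, the T3 t-test rejects 6.8% at 5% missing, 7.7% at 10%, 11.6% at 20% and 15.6% at 30%. In this milder setting (20% missing at T3, none at T2) the group-by-visit test rejects 7.6-8.7% with group in the model.

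**5. Shrinkage when group is left out.** Take a true 0.5 SD difference at T2 and T3 and none at T1. Of the 6 per group missing T3, 3 also miss T2 and are predicted from T1 alone, which carries no group difference. The average T2 difference available to the imputation is 3/6 x 0.5 = 0.25. The coefficient of T3 on T2 given T1 is about r/(1 + r): 0.167 at r = 0.2 and 0.333 at r = 0.5. The T3 difference after imputation is then:

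- r = 0.2: 0.8 x 0.5 + 0.2 x 0.167 x 0.25 = 0.408
- r = 0.5: 0.8 x 0.5 + 0.2 x 0.333 x 0.25 = 0.417

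Simulation agrees, at about 0.41-0.42 SD.

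**6. What a proper method gives.** With 20% missing at T3 only and correlation 0.2, multiple imputation (20 sets, group in the model, Rubin pooling) gave 5.2% for the T3 t-test. Complete cases gave 5.3%. Multiple imputation without group gave about 1%, which is too conservative, so pooling alone is not enough.

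**The case against.** A reader might infer that the plan treats filled-in values as observed and so runs at a false-positive rate of 10-13%. The documents do not support that.

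- Single imputation is nowhere stated. The text is silent, and the SPSS routine it names is not described. Silence permits single imputation but does not establish it.
- The inflation of between-group tests needs group in the imputation model. Section 17.5 draws its predictors from demographic and dependent variables related to dropout; group appears only in the chi-square step. Read literally, group may be absent, and those tests then stay near 5%. The error therefore cannot be separated from the choice of predictors.
- The 20% missing at T3 is an assumption, and at 10% the T3 t-test rate is under 8%. The quantity that 17.4 powers, the three-visit average, reaches only about 6-8%.
- A completer comparison is planned, and a mixed model is only one valid remedy. It does not cover the yes/no executive-function items in 4.1.3 and 6.7.

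All of this stands as a limit on the size of the claim. It does not rescue the plan. Leaving group out exchanges inflated between-group tests for a diluted group difference, and the ANOVA visit effect, which bears on the within-participant comparison in 17.1, stays inflated. The completer comparison changes no standard error and removes no dilution.

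**Conclusion.** The concern holds in conditional form. Section 17.5 passes imputed values to standard tests and leaves open the two choices that decide whether those tests are valid: how imputation uncertainty is carried, and whether group is in the model. If imputation is single, with the assumed dropout and alpha, both settings of the second choice do harm. With group, the T3 t-test and group-by-visit test run at roughly twice the nominal 5%. Without group, the visit effect does so, and the T3 difference loses about 16-18% of its size (0.42/0.50 = 0.84; 0.41/0.50 = 0.82).

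The size rests on random dropout, 30 per group and correlations of 0.2 to 0.5, and it grows or shrinks with the missing fraction, which the plan never estimates. If the sponsor already intends multiple imputation with group and pooling, the problem is one of wording. The point should be settled before analysis, since all three Aim 1 hypotheses depend on these tests.

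**What to change.** For each continuous measure, replace repeated measures ANOVA on imputed data with one linear mixed model fitted by REML to all observed visits. Use fixed effects for group, visit and group-by-visit and an unstructured covariance over T1 to T3, and take the between-group contrasts from that model. No value is filled in, and sphericity is not needed.

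For the yes/no items, or if imputation is kept as a sensitivity analysis, specify multiple imputation with at least 20 sets, with group and earlier visits in the imputation model (besides any variables related to dropout) and Rubin pooling. The completer comparison can stay as a description, but the SAP should not treat it as a correction.

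The cost is SAP wording and a different procedure, with no new data. Intervals will be somewhat wider than under single imputation, because they then reflect the data that were actually collected.

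### Agreement between completer and imputed results in 17.5 cannot rule out a sizeable bias from dropout related to unseen performance, and the plan has no analysis that can.

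*Combined protocol and SAP*

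**What the plan says.** Section 17.5 handles missing data in three steps. First, "the dropout rates will be compared across the groups with chi-square analyses to assess systematic differences due to condition". Second, demographics and outcome measures are examined for a relation to dropout, and those found related are used to impute. Third, "comparison of the completers vs. imputation analyses will yield an additional estimate of the effect of dropouts on hypothesis tests". The section gives no expected dropout rate, no assumption about why values are missing, and no analysis under a not-at-random assumption. None appears elsewhere in the document.

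The only between-visit correlation is in the power analysis (17.3/17.4): "Assuming a correlation of 0.2 across the repeated measures at three time points". Section 6.1 sets the size: "We will recruit N=60 participants total", split 30 and 30.

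**The concern.** Imputed values are generated from relationships seen among people who were observed. If a user has no T3 drive for reasons tied to how that user would have driven at T3, neither the completers nor the imputation model carries that information beyond what measured variables explain. Both estimates are then biased in the same direction and by nearly the same amount, and their agreement is uninformative about that bias.

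This matters because Aim 1 hypothesises poorer driving in users, and use is self-chosen and unblinded. The protocol also leaves routes by which a poor visit could become a missing one: a drive is ended for motion sickness (18.1), any procedure may be skipped (19.1), and participants may withdraw (22.1). If the worse-performing users are the ones missing, the group difference shrinks toward zero. A null on driving could then be described as robust to dropout although that was never tested. A better-specified imputation model does not remove the problem, since the check below already imputes from group, T1 and T2.

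**Working it through.** **1. The plan's own figure.** With correlation 0.2, the SD of a three-visit average is √((1 + 2×0.2)/3) = √(1.4/3) = 0.683, which matches "the standard deviation of the average of three measures is 0.683 times the standard deviation of one measure". The standardised effect is 0.5/0.683 = 0.732. With a two-sided alpha of 0.05 (assumed, as the plan gives no alpha), noncentral-t power is 0.796 at 30 per group and 0.809 at 31. The stated 31 per group reproduces, so 0.2 is the common correlation between visits.

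**2. What earlier visits can tell the imputation.** With a common correlation ρ, R² of T3 on T1 and T2 is 2ρ²/(1+ρ) = 2×0.04/1.2 = 0.067. On T1 alone it is ρ² = 0.04.

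**3. Simulation inputs.**
- From the documents: 30 per group, correlation 0.2, effect 0.5 SD of one measure (placed at T2 and T3).
- Assumed: the dropout rates; a user's chance of being lost at T3 either constant (harmless) or proportional to exp(own T3 value in SD, higher meaning worse); random dropout in controls; agreement defined as a gap under 0.1 SD.
- T3 is imputed by regression on group, T1 and T2.

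**4. T3 contrast, true difference 0.50 SD.**

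| User dropout | Mechanism | Completers | Imputed | Lost (completers) |
|---|---|---|---|---|
| 30% (controls 10%) | harmless | 0.50 | 0.50 | none |
| 30% (controls 10%) | outcome-related | 0.22 | 0.23 | (0.50−0.22)/0.50 = 56% |
| 20% | outcome-related | 0.31 | 0.32 | (0.50−0.31)/0.50 = 38%; 37% in a repeat run |
| 15% | outcome-related | 0.35 | 0.36 | (0.50−0.35)/0.50 = 30%; about 25% in a repeat run |

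At 15% the result is sensitive to rounding, since 15% of 30 is 4.5 users. In the 30%/10% case the two estimates lie within 0.1 SD in 93% of trials under harmless dropout and 91% under outcome-related dropout (96% and 95% in another run).

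**5. A harsher mechanism with 17.5's own rule.** Here the worst-performing users leave, and multiple imputation uses only variables found related to dropout. At 20% user dropout, completers/imputed are 0.49/0.50 when harmless and 0.16/0.17 when the worst leave. The two are within 0.1 SD in 98.8% of trials in both cases. At 10% dropout the worst-first figures are 0.31/0.31.

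**6. Where the point weakens.**
- *Three-visit average*, 30%/10% dropout, mechanism as in step 4, true value (0+0.5+0.5)/3 = 0.33 SD: the loss is 37% (completers) and 24% (imputed), or 41% and 28% in another run. Agreement is 73% under outcome-related dropout vs 77% under harmless dropout.
- *T1-to-T3 change*, same dropout: agreement is 61% vs 63%, so it is far from automatic in either case.
- *Higher correlation*: at 0.5, agreement on T3 is 56% vs 76%. With 20% worst-first loss and earlier visits always used, the mean gap grows from 0.016 SD at correlation 0.2 to 0.080 at 0.5 and 0.199 at 0.8.

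**7. The other two steps of 17.5.** Exact enumeration at 30 per group gives chi-square power of 50% for 10% vs 30% dropout (37% with continuity correction) and 19% for 10% vs 20%. A stark imbalance would be flagged: for 6/30 vs 0/30, chi-square = 60×(6×30)²/(30×30×6×54) = 6.67, p about 0.01. If 20% leave in each arm, worst-first in users and at random in controls, the rates are equal. The search for variables related to dropout then finds one in only about 14% of trials.

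**The case against.** The strongest reply is that this is a general limit of any imputation that assumes missingness is explained by observed data, in a 60-person observational study, and that the numbers rest on inputs the protocol does not give. Much of that stands. The dropout rates, selection strength and 0.1 SD margin are all assumed. The 0.2 is a planning value, and at higher correlations the comparison becomes informative. Aim 1 uses repeated measures ANOVA over all three visits, and the power statement concerns their average, so the T3 contrast is the case in which agreement is easiest. Step two of 17.5 could also bring in predictors that the simulation does not have.

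A reader might infer three stronger things that the documents do not support:
- That dropout would remove over half the effect. In the step 4 runs this happens only at an assumed 30% user dropout on T3; worst-first loss gets there at 20%, and no rate or pattern is stated.
- That the two analyses agree equally well whatever is analysed. For the three-visit average, agreement is somewhat lower under biasing dropout, and for change it is well short of automatic.
- That 17.5 declares dropout harmless when the two results agree, or when the chi-square is non-significant. It calls the comparison an additional estimate and states no such rule. Nor does any section say that impaired users will miss visits.

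What the reply does not supply is an analysis that addresses dropout related to unseen performance.

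**Conclusion.** The point holds in limited form. The third step of 17.5 is presented as estimating the effect of dropouts, but it can estimate only the part explained by measured variables. At the plan's correlation of 0.2 that part is small. For the T3 contrast, a loss of about 25%, 37% and 56% of a 0.5 SD difference (15%, 20% and 30% user dropout, selection of log-weight 1 per SD) goes with an average gap of only 0.01 to 0.02 SD between the two analyses. For the three-visit average the loss at 30% dropout is about 24% to 37%.

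These sizes illustrate what could go unseen. They do not predict what will happen. Agreement cannot rule out a sizeable not-at-random bias, the chi-square is too weak at this sample size to compensate, and equal dropout rates do not show equal reasons. This is an inexpensive improvement worth making, because it governs what a null on driving performance can be said to show.

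**What to change.** In 17.5:

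- State that comparing completers with imputed results reflects only dropout explained by measured variables.
- Add a delta-adjusted (tipping-point) sensitivity analysis for the Aim 1 outcomes. Shift the imputed T2 and T3 values of marijuana users toward poorer performance in fixed steps, and report the shift at which the conclusion changes. For continuous outcomes such as braking and response times, steps from 0 to 1.0 SD would serve. For yes/no items and for omission and commission counts, apply the shift on the log-odds or log-rate scale, since SD steps have no clear meaning there.
- Report dropout by group as a difference with a 95% confidence interval, with reasons, and do not read a non-significant chi-square as absence of a systematic difference.

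The cost is one revised paragraph and a few re-runs of the imputed analysis, with no new data, visits or participants. The downside is that a reported result may be shown to depend on the dropouts.
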